10.0 Quality Control and Quality Assurance

We will employ several quality control procedures namely written protocols, training, objective evaluation of tDCS protocols and training research personnel thus maximizing validity and reliability of the protocol delivery and outcome assessments.

As a part of the subject's tDCS kit, a tDCS side effects survey checking for typical side effects that may arise during or after tDCS will be included. Subjects would be instructed to record the presence/absence of each side effect, the severity and duration. Any side effect that is rated very

severe and atypical of tDCS, regardless of whether the subject attributes to tDCS or not, should be reported and assessed by study personnel before further treatment is continued. Guidelines provided to participants can help identify and document adverse events that may be useful in managing any potential risks. In addition, the information guide provided to the subject will minimize any risk of harming themselves or damaging the tDCS device.

To monitor compliance, we will also ensure that participants are familiar with basic functioning of a smart phone/laptop/computer/iPad and how to connect the device to internet via a computer aptitude checklist (Supplement_technical aptitude checklist). We will also ensure that participants have the aptitude to setup the tDCS device. We will choose a secure video conferencing software such as Zoom PHI to allow for remote supervision of the proper setup of the device, optimal electrode-skin contact, and that the intender user is receiving the treatment.

Assessors who are performing the clinical assessments will be blinded to the intervention. [name] will be actively involved with supervising and monitoring the study on a day-to-day basis. She will meet with all study personnel at least once a week to ensure that there is strict adherence to study protocol and outcome assessments. [name] will also hold bi-monthly journal club meetings to ensure that all key personnel are abreast of the scientific literature in the area and the importance of the current research and thereby motivate staff to ensure their best performance during training and assessment. All key research personnel will be provided the adequate training and equipment needed to carry out the study. Training will be repeated as necessary. [name] will check and regularly review any adverse events or deviations from protocol. Study personnel will monitor subject compliance to the protocol and losses to follow up.

11.0 Data and Safety Monitoring

The PI will be primarily responsible for monitoring the safety of participants, and the safety and confidentiality of data. This will be done by following the best practices to ensure that we strictly adhere to the inclusion and exclusion criteria, and protections against risks outlines. The safety of each participant will be assessed on an individual basis throughout his or her involvement with the study, regardless of group assignment. Any decline in function or participant responses that indicates a potential adverse effect will be reviewed individually.

A member of the research team will be available to the subject throughout testing and will be monitoring subject safety throughout. We will ask the subject to provide us with a phone number of a caregiver (or friend or family member) to contact in case of emergency. For the RS-tDCS, the stimulation sessions will be supervised remotely from the research lab using video conferencing. The RS-tDCS device has built in programmable codes which allows for strict dosage control which can be monitored remotely. The device would be deactivated until a code is provided by the research staff to the subject for every session. The code unlocks a single session with a pre-set duration and intensity. After a single discharge, the device is inert until a new code is provided. This allows the remote supervisor to control RS-tDCS application, as the code may not be provided until the researcher is satisfied with the placement of the electrodes via video or phone conference. The subject or caregiver cannot change stimulation intensity or treatment duration which enhances safety and reproducibility. The subject will also be asked to report adverse effects at the beginning and end of every session. The subject cannot operate the

device unless there is another adult present at home in case they are alone and an AE occurs and they are unable to call for help. Participants will be instructed to contact the Emergency Department in the event of experiencing serious side effects.

Before sending the device home, at the training visit, study personnel will complete a tDCS checklist to screen subjects for suitability of RS-tDCS. This will be double checked by the Principal Investigator prior to release of the device to the subject. If the subject qualifies, we will ensure a rigorous training session for the subject and if necessary, the caregiver. We will instruct the subjects to maintain a RS-tDCS log which will be reviewed by staff every 2 weeks until the end of the study. We have many different stops inserted into the protocol for the safety of the participant. The STOP criteria are summarized below:

- tDCS tolerability test – Stop 1: Does not pass tDCS tolerability test, has pain or other adverse effects
- tDCS training visit – Stop 2: Does not understand tDCS
- RS-tDCS sessions:
 - Zoom PHI video call – Stop 3: Three reschedules/ failure to initiate conference
 - Placement of headset: Stop 4: Failure to place headset correctly within 30 minutes at more than one study session
 - Adverse event – Stop 5: Subject reports experiencing any of the critical events
 - Pain- Stop 6: Reporting of a pain score of 7/10 or more at any point
- In addition, a pre-specified interim analysis for the continuation of the entire study will be completed after the first 6 participants complete the study. The adverse events and mean change in ALSFRS-R between the 2 groups will then be compared. The stopping criteria will be defined as a mean difference between groups exceeding 2 standard deviations. If this occurs, the study will be stopped for full review by the medical monitor or revising the protocol before proceeding

[name] will serve as the medical monitor of the study. A DSMB will be established to monitor the study in terms of timely subject enrollment, integrity of data acquisition and storage, and patient safety. There will be three members who will not be a part of the study team, and who will have no conflicts of interest. The DSMB will include a physician, a scientist with clinical trials experience, and a physical or occupational therapist with experience in working with patients with neurological conditions. Adverse events and unanticipated problems will be reported within 24 hours to the IRB and documented on an Adverse Event Log Sheet in the research records.

12.0 Statistical Considerations

Subjects and their caregivers face difficulties in participating in randomized controlled trials. Some of the issues that limit participation include travel arrangements, travel associated costs, caregiver's time and scheduling of multiple appointments. Hence it is critical to perform a thorough assessment of the potential benefits of RS-tDCS before considering a randomized controlled trial (RCT). We have powered the study to demonstrate safety of RS-tDCS in terms of adverse events. We will study 100 subjects with ALS. For Aim 2, we will be testing 50 subjects per group. For each comparison of 50 subjects with RS-tDCS compared to 50 in the other group, if the true adverse event rates are really equal, we will have 80% power to reject the null of a

higher event rate in the RS-tDCS group. This power will also obtain an estimate of the variance of the treatment effect for use in power calculations for a future study. We have estimated a total of 100 subjects to be included in the study.

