
Need for remotely delivered tDCS: Several clinical trials have shown that multiple tDCS sessions are required to produce greater benefits in clinical outcomes, especially in clients with limited motor recovery, where tDCS related effects are thought to be cumulative (Acler et al., 2013; Ferrucci et al., 2014; Meesen, Thijs, Leenus, & Cuypers, 2014; Mori et al., 2010; Mori et al., 2013; Rosso et al., 2014). Most tDCS based studies thus far have been conducted in a laboratory-based setting. There are several barriers for accessing tDCS based studies. Repeated tDCS application requires participants to travel to the lab for each treatment session, which can be burdensome to patients and their caregivers. Especially because the tDCS sessions last only for 20 minutes and the participants have to spend anywhere between 2-3 hours to travel for this session (Brunoni, Ferrucci, et al., 2012; Brunoni, Nitsche, et al., 2012; Ferrucci et al., 2014; Holland & Crinion, 2012; Meesen et al., 2014; Vaseghi, Zoghi, & Jaberzadeh, 2014). Some studies have reported significant drop-out rates when participants were treated with tDCS sessions that were administered over 6 months (Loo et al., 2012; Martin et al., 2013). Moreover, when the target population has a progressive neurological disorder such as ALS, there is a higher drop out as reported in several intervention-based studies (Bello-Haas et al., 2007; Sanjak, Bravver, Bockenek, Norton, & Brooks, 2010). Patients receiving palliative care often rely on their caregiver and may not comply with traditional research protocols. This causes ineffective data collection and underpowered tDCS studies which reduce the generalizability of this promising device.

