4.0 Eligibility

4.1 Inclusion Criteria

The general inclusion criteria will be approximately 100 males and females of any race or ethnic status with the following characteristics:

- Age between 18 – 80 years
- Diagnosis of possible, probable, or definite amyotrophic lateral sclerosis according to El Escorial revised criteria
- Spinal onset ALS with initial weakness in the upper or lower extremity.
- Diagnosed with ALS within the past 5 years
- 1-2 point change in pre-slope of the ALSFRS-R at time of enrollment (ratio of drop in score from 48 to the duration in months from onset of weakness)
- Score ≥ 2 for “swallowing” of the ALSFRS-R
- Score ≥ 2 for “walking” of the ALSFRS-R
- Able to provide informed consent
- Stable dose of riluzole, edaravone, AMX0035 (Relyvrio) or no medications
- Availability of a caregiver for remote administration of tDCS

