9.0 Data Analysis

We will look at pre and post changes in our primary and secondary outcomes measures. A one-way ANOVA will be used to examine changes in adverse events, subject dropouts, and TMS and clinical assessments. A two-way repeated measures ANOVA with groups and time as the two factors will be used to analyze change scores on adverse events, TMS and clinical assessments.

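### Section 12 counts all 100 enrolled participants as compared, with no allowance for loss and no analysis set; if leavers fall out, the adverse-event comparison can be biased and has less than the stated 80% power

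*Combined protocol and SAP*

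**What the plan says.** Section 4.1 sets enrolment: "The general inclusion criteria will be approximately 100 males and females of any race or ethnic status". Section 12.0 repeats the total ("We will study 100 subjects with ALS"), gives the size for the efficacy aim ("For Aim 2, we will be testing 50 subjects per group"), and rests its only power claim, 80% for adverse events, on the same numbers: "For each comparison of 50 subjects with RS-tDCS compared to 50 in the other group, if the true adverse event rates are really equal". No section states a drop-out rate, an evaluable number, an analysis set or a rule for missing data.

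Section 2.0 (need for remotely delivered tDCS) describes retention in this setting: "Some studies have reported significant drop-out rates when participants were treated with tDCS sessions that were administered over 6 months", and "when the target population has a progressive neurological disorder such as ALS, there is a higher drop out as reported in several intervention-based studies". It gives no rates. It goes on to say that such difficulties leave tDCS studies underpowered.

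Section 9.0 plans a one-way ANOVA on changes in adverse events, dropouts, TMS and clinical assessments, and then: "A two-way repeated measures ANOVA with groups and time as the two factors will be used to analyze change scores on adverse events". The same model is to be applied to the TMS and clinical outcomes. Sections 6.0 and 11.0 list stop criteria for individual participants, among them not tolerating tDCS, serious or critical adverse events, and a high pain score. Section 6.0 schedules assessments at entry, 12 weeks, 24 weeks and a 3-month follow-up, and has adverse effects asked about at the start and end of every session.

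**The concern.** A sample size that equals enrolment is adequate only if everyone reaches the analysis, or if the analysis is defined so that leavers still count. Section 12.0 shows neither, and the protocol's own background describes drop-out as a known difficulty.

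Two things are at stake. The first is bias. Change scores and a conventional repeated measures ANOVA need later values, and some participants will lack them because they were stopped for an adverse event, intolerance or pain. Leaving them out removes the most informative people from the one endpoint for which power is claimed. The second is the stated figures. A finding of no excess of adverse events would be presented as coming from a comparison with 80% power when fewer people were compared. Likewise, 50 per group for the 24-week and follow-up outcomes is a best case.

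**Working it through.** **Inputs.** From Section 12.0: 50 v 50, 80% power, equal true event rates. From Section 4.1: about 100 enrolled. Not in the documents, so assumed: one-sided alpha of 0.05 or 0.025, and loss d of 10%, 20% or 30%.

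**Step 1: the plan's own 80%.** With equal true rates, a superiority test would have power equal to its one-tail alpha (2.5% to 5%), so only a non-inferiority reading makes sense. The margin that gives 80% power with n per group and event rate p is

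margin = (z_alpha + z_0.80) × √(2p(1−p)/n).

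At n = 50 and p = 20%, one-sided 0.05: (1.645 + 0.842) × √(0.32/50) = 19.9 percentage points.

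| Event rate | Margin, one-sided 0.05 | Margin, one-sided 0.025 |
|---|---|---|
| 10% | 14.9 points | 16.8 points |
| 20% | 19.9 points | 22.4 points |
| 50% | 24.9 points | 28.0 points |

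So 80% at 50 per group is attainable, but the documents do not say which case applies. The figure cannot be reproduced; it is taken as given below.

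**Step 2: power if leavers are excluded.** If 80% holds at 50 per group, then with n = 50(1−d) per group, under the normal approximation,

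power = Φ[(z_alpha + z_0.80) × √(n/50) − z_alpha].

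The margin and event rate cancel. Example, one-sided 0.05, d = 20%: n = 40; 2.487 × √0.8 = 2.224; 2.224 − 1.645 = 0.579; Φ(0.579) = 71.9%.

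| Assumed loss | n per group | Power, one-sided 0.05 | Power, one-sided 0.025 |
|---|---|---|---|
| 0% | 50 | 80.0% | 80.0% |
| 10% | 45 | 76.2% | 75.7% |
| 20% | 40 | 71.9% | 70.7% |
| 30% | 35 | 66.8% | 65.0% |

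Exact binomial enumeration of the Wald non-inferiority test (20% event rate, 19.9-point margin, one-sided 0.05) agrees closely: 80.5%, 76.8%, 72.8% and 68.2% at 50, 45, 40 and 35 per group.

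**Step 3: power if leavers are counted.** If every treated participant enters the adverse-event comparison, n stays at about 50 per group and power does not fall through n. The whole loss in Step 2 therefore depends on the analysis set, which the plan does not define.

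**Step 4: outcomes that need a later visit.** For 24-week and follow-up ALSFRS-R and TMS values, someone who has left has no value at that visit. At 20% loss, 50 × 0.8 = 40 per group are evaluable (45 at 10%, 35 at 30%). To have 50 evaluable at 20% loss would take 50/0.8 = 62.5, so 63 per group. This shows the scale only; an increase is not proposed.

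**The case against.** The strongest reply is that the only powered endpoint is adverse events, and these are asked about at every session. A participant who leaves has contributed data up to that point, and no section excludes leavers. Section 9.0 also compares dropouts, which cannot be done in completers alone. This stands: the loss of power is conditional. It does not settle the matter, because collecting events is not the same as analysing them. Both analyses in Section 9.0 are framed on changes or change scores, and no analysis set is named.

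A reader might infer that the protocol itself expects heavy drop-out, so that the 80% is definitely not delivered. The documents do not support that. Section 2.0 reports drop-out in earlier studies, gives no rate, and uses it to argue for home delivery, which Sections 1.0 and 2.0 expect to help adherence and compliance. Section 2.0 also cites a remote pilot in multiple sclerosis with 20 participants and 192 sessions and no discontinuation, although over two weeks rather than 24. Drop-out is itself a feasibility outcome here. And since the 80% lacks a margin, alpha and event rate, there is no verified baseline from which to subtract.

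Two further limits are fair. Sham lasts only 12 weeks, so losses after that bear less on an active-versus-sham comparison of adverse events. The documents also do not say whether randomisation precedes the tolerability test, so early stops may not all be losses from 50 v 50. Finally, Aim 2 has no stated power; its 50 per group is a group size, not a power claim that fails.

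**Conclusion.** The point holds in conditional form. The plan counts all enrolled participants as compared, allows for no loss and defines no analysis set, in a setting where its own background reports drop-out. If Section 9.0 is run in the usual way, participants without later values are dropped, including those stopped for adverse events, intolerance or pain. The adverse-event comparison is then open to bias and has about 76% power at 10% loss, 71-72% at 20% and 65-67% at 30%. These figures assume that 80% at 50 per group is correct, that loss is equal in the two groups, and that the loss rates, which the documents do not give, are as assumed. The missing margin, alpha and event rate are a separate and more basic defect in the same sentence of Section 12.0. For the 24-week and follow-up ALSFRS-R and TMS comparisons, 50 per group is a best case whatever is decided for adverse events, unless a method for missing values is specified.

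**What to change.** Keep N = 100 and make three changes.

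1. In Section 9.0, compare adverse events between groups in every participant who received at least one home session, counting events up to the time of leaving, in place of change scores that need later values.
2. In Section 12.0, say that the 80% refers to this all-treated comparison, and that it would be about 71-72% at an assumed 20% loss if only completers were compared. Once change 1 is adopted, the lower figure does not apply to the adverse-event comparison and should not be quoted as its power.
3. For the 24-week and follow-up ALSFRS-R and TMS comparisons, replace 50 per group with 50 randomised and about 40 (35-45) expected evaluable per group at an assumed 20% (10-30%) loss.

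The cost is a few sentences and slightly less favourable stated figures. No extra participants or visits are needed.

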13.0 Regulatory Requirements

13.1 Informed Consent

Oral consent will be obtained by phone during the initial telephone screen. Upon determination of eligibility, the initial meeting will take place in Room 810 in the Applied Health Science Building ([name]) Subjects will meet with [name] and/or key research personnel who will explain the research study. Subjects and/or family will then review the informed consent document and all questions will be answered by the investigator. Informed consent will be obtained in English using lay language. The subject will receive a copy of the signed informed consent document and the investigator will keep the original in the research records. A preparatory to research waiver will be secured by the IRB according to 45 CFR 46 164.512(i)(1)(ii). A waiver of informed consents for the screening, recruiting, and determining eligibility will be secured by the IRB according to 45 CFR 46.116(g).

13.2 Subject Confidentiality

Screening and testing of participants will be conducted in private rooms. Subject's privacy will be protected at all times by ensuring that only key research personnel are present during testing and training. An alphanumeric code will be used to identify each subject. Authorized research personnel will maintain a master sheet which has the subject's name linked to his/her code (initials followed by a number). This sheet will be maintained on the lab computer in a password protected file that only the research team directly working on the project has access to. The other data will be maintained on the lab computers which only authorized personnel have access to. Security of these computers are maintained by the College of Applied Health Science IT personnel. The key linking the code to the subject's identity will be destroyed 10 years after study completion. Results published will not include names of subjects.

13.3 Unanticipated Problems

Any unexpected experience, adverse events or outcomes related to the research will be closely monitored by the research personnel and reported to [name] immediately. [name] will take necessary action according to the nature of unforeseen problem which will suspension of research procedures in currently enrolled subjects; modification of research procedures for new subjects; changes of the informed consent document/process to ensure subject safety and privacy, modification of inclusion or exclusion criteria to mitigate the newly identified risks; implementation of additional procedures for monitoring subjects; and/or suspension of enrollment of new subjects.
